## **9.5. Cutaneous Reaction Assessment**

A summary of the cutaneous reaction assessments (CRAs) will be provided using the safety population. The number and percentage of subjects falling into each severity category (None (1), Mild (2), Moderate (3), Severe (4), Not Applicable (5)) for reactions of Erythema, Induration, Swelling, Blister Formation, Desquamation, Erosion, Ulceration, and Necrosis will be provided in the summary.

The summary will present reaction within scheduled visit (W1D2, W1D3, W1 Safety Assessment, W2D1, W2D2, W2D3, W2 Safety Assessment, Limited Safety Assessment, EOT, EOS 1 Week Post-excision, EOS 2 Weeks Post-excision) within lesion (TL1, TL2, NTL1, NTL2, NTL3).

A separate listing will be provided for CRAs using the safety population, and this listing will include whether a CRA was Performed (Yes, No), Visit, Date Assessment Performed, and reaction assessments as described above.

A separate listing will also be provided for Photo Assessment using the safety population, and this listing will include Visit, Lesion Photos Taken (Yes, No), Date and Time of Photos, and Photos Uploaded (Yes, No).

## **9.6. Dermatologic and Physical Examinations**

A dermatologic examination including Fitzpatrick Skin Type is to occur at screening, and a limited physical examination of the following body systems may occur at scheduled visits (Screening, W1D1, W1D2, W1D3, W1 Safety Assessment, W2D1, W2D2, W2D3,

W2 Safety Assessment, Limited Safety Assessment, EOT – not all body systems are examined at all scheduled visits) or for symptom or AE-directed reasons.

- General Appearance
- Head, Ears, Eyes, Nose, Oral, Throat
- Respiratory
- Cardiovascular
- Gastrointestinal
- Genitourinary
- Musculoskeletal
- Neurological
- Lymphatic
- Skin
- Reproductive
- Endocrine
- Other

Separate listings will be provided for Dermatologic and (Limited) Physical Examinations using the safety population. The Dermatologic Examination listing will include Exam was Performed (Yes, No), Visit, Date Exam Performed, Clinically Significant (Yes, No), Description, and Fitzpatrick Skin Type (I-VI). The (Limited) Physical Examination listing will include Exam was Performed (Yes, No), Visit, Date Exam Performed, Body System Examined, Result (Normal, Abnormal, Not Done), and Abnormal Findings.

No summary tables will be provided. Fitzpatrick Skin Type (I-VI) is summarized in the Demographics and Baseline Characteristics display described in Section 7.3 of this SAP.

## **9.7. Pregnancy Tests and Partner Pregnancy**

Partner pregnancy is to be reported for all subjects at screening, and only females of childbearing potential are tested for pregnancy. Urine pregnancy tests are to be performed prior to W1D1 and W2D1 injections. Serum-based pregnancy tests are to be performed at other scheduled visits (Screening, W1 Safety Assessment, W2 Safety Assessment, EOS 1 Week Post-excision, EOS 2 Weeks Post-excision – not all laboratory parameters are collected at all scheduled visits).

Verrica Pharmaceuticals Inc.  
Protocol: VP-315-201

Statistical Analysis Plan  
6-Sep-2024

Separate listings will be provided for Pregnancy Tests and Partner Pregnancies using the safety population. The Pregnancy Tests listing will include Visit, Test Performed (Yes, No), Date of Test, Laboratory Test Name, Test Type (Serum, Urine), and Result (Positive, Negative). The Partner Pregnancies listing will include Visit, Date of Visit, and whether Subject Shared Partner is Pregnant (Yes, No).

No summary tables will be provided.

## 10. Treatment Satisfaction Analysis

The conventions of Section 5 of this SAP will be applied. Tables and figures will be prefixed with 14, and listings will be prefixed 16. Tables will be provided for Part 1 and Part 2 unless noted otherwise.

### 10.1. SCAR-Q – Appearance Scale

A summary of SCAR-Q – Appearance will be provided using the full analysis population. Descriptive statistics will be provided for Raw Sum (12 = Best to 48 = Worst), Rescored Sum (12 = Worst to 48 = Best), and Score (0 = Worst to 100 = Best). The number and percentage of subjects falling into each scale level (1 = Not at all, 2 = A little, 3 = Quite a bit, 4 = Very much) for responses to the following twelve “How much are you bothered by...” assessment questions will be provided in the summary:

1. How your scar looks from far away
2. How wide your scar looks
3. How your scar looks from different angles
4. How thick your scar looks (more raised than you would like)
5. The length of your scar
6. The surface of your scar (more bumpy than you would like)
7. The color of your scar
8. The difference between the color of your scar and your skin color
9. The contour of your scar (not as flat as you would like)
10. The overall size of your scar
11. How your scar looks close up
12. How noticeable your scar is

Raw Sum is calculated as follows:

- If the number of missing responses is 0, then Raw Sum is the total of the numeric response values.

- If the number of missing responses is  $>0$  and  $<6$ , then Raw Sum is  $[(\text{number of missing responses} \cdot \text{mean of non-missing response}) + \text{total of non-missing numeric response values}]$ .
- If the number of missing responses is  $\geq 6$ , then Raw Sum is missing.

Rescored Sum is calculated as follows:

- Each non-missing numeric response value is transformed into  $5 - \text{response value}$ .
- Then proceed the same as for Raw Sum, except use transformed response values.

Score is calculated as follows:

- If Rescored Sum is missing, then Score is missing.
- Otherwise, Score is provided by the SCAR-Q Conversion Table.

The summary will present Raw Sum, Rescored Sum, Score, and the above listed questions within scheduled visit (W1 Safety Assessment, W2 Safety Assessment, EOT).

A separate listing will be provided for SCAR-Q – Appearance using the full analysis population, and this listing will include Visit, Date of Visit, and the parameters as described above.

Only Part 2 will be summarized.

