#### 11. STATISTICAL CONSIDERATIONS

#### 11.1 General Considerations

A statistical analysis plan (SAP) will be provided that gives a complete description of the statistical methods to be used in this study. The SAP will describe the methods and data presentation to be used for the analysis of safety, efficacy, and PK outcome data. If analyses in the SAP do not align with the analyses described here, the SAP will identify where those methods differ.

Analyses will be carried out by study part (Part 1 and Part 2). For Part 1 and Part 2, an overall summary will be provided. More detail will be provided in the SAP.

Descriptive statistics for continuous variables will include number of subjects, mean, standard deviations, median, minimum, and maximum. Counts and percentages will be provided for categorical/ordinal variables. Unless specified otherwise, denominators for percentages will only consider non missing responses. For any summaries that involve change from baseline, baseline will be defined as the last measurement obtained prior to first injection of study drug. By-subject listings for all subjects will be provided for data collected.

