## **6. Analysis Populations**

**Enrolled Subjects:** Enrolled subjects are subjects who signed the informed consent form and were not screen failed. Enrolled subjects will serve as the population for certain analyses as described in this SAP.

**Safety (SAF) Population:** The Safety Population will include all subjects who received at least one injection of VP-315. The SAF Population will serve as the primary population for the analysis of safety-related data.

**Full Analysis (FA) Population:** The Full Analysis Population will include enrolled subjects who received one full dose (actual equals expected for at least one treated lesion) of VP-315 (for Part 1 and Part 2 Cohorts 4 and 5, a full dose consists of two injections) and have at least one non-missing post-baseline efficacy observation for histologic clearance of lesions at excision (see Section 8 of this SAP for details). The FA Population will serve as the primary population for the analysis of efficacy-related data.

**Per-protocol (PP) Population:** The Per-protocol Population will include FA subjects who have no major protocol deviations that may substantially affect the results of the efficacy analyses outlined in Section 8 of this SAP. The final determination on protocol violations, and thereby the composition of the PP, will be made before database lock.

The PP Population will be used as the secondary population for the efficacy analyses outlined in Section 8 of this SAP.

A non-exhaustive list of potential major protocol deviations is provided below:

- Investigational Product Deviations
  - Subject received wrong treatment
  - Deviation in IP storage
  - Error in IP dosing
- Enrollment Deviations
  - Subject is enrolled prior to determining whether eligible for study
  - Ineligible subject is enrolled
  - Enrollment occurs outside protocol window
- Study Data and/or Forms Deviations
  - Forms or data not sent from clinical site to coordinating center
  - Missing data and/or form
  - Missing images and/or operative reports
- Subject Deviations
  - Subject administration of a prohibited medication
  - Subject compliance with protocol
  - Subject met withdrawal criteria but was not withdrawn
- Visit/Procedure Schedule Deviations
  - Visit/Procedure not completed
  - Visit/Procedure not completed in window

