## 10.2. FACE-Q – Psychological Function

A summary of FACE-Q – Psychological Function will be provided using the full analysis population. Descriptive statistics will be provided for Raw Sum (10 = Worst to 40 = Best) and Score (0 = Worst to 100 = Best). The number and percentage of subjects falling into each scale level (1 = Definitely disagree, 2 = Somewhat disagree, 3 = Somewhat agree, 4 = Definitely agree) for responses to the following ten assessment statements will be provided in the summary:

- a. I like myself
- b. I feel positive about myself
- c. I feel okay about myself
- d. I feel happy
- e. I am comfortable with myself
- f. I am accepting of myself

Verrica Pharmaceuticals Inc.  
Protocol: VP-315-201

Statistical Analysis Plan  
6-Sep-2024

- g. I feel good about myself
- h. I feel confident
- i. I feel attractive
- j. I feel great about myself

Raw Sum is calculated as follows:

- If the number of missing responses is 0, then Raw Sum is the total of the numeric response values.
- If the number of missing responses is  $>0$  and  $<5$ , then Raw Sum is  $[(\text{number of missing responses} \cdot \text{mean of non-missing response}) + \text{total of non-missing numeric response values}]$ .
- If the number of missing responses is  $\geq 5$ , then Raw Sum is missing.

Score is calculated as follows:

- If Raw Sum is missing, then Score is missing.
- Otherwise, Score is provided by the FACE-Q Conversion Table.

The summary will present Raw Sum, Score, and the above listed statements within scheduled visit (W1 Safety Assessment, W2 Safety Assessment, EOT).

A separate listing will be provided for FACE-Q – Psychological Function using the full analysis population, and this listing will include Visit, Date of Visit, and the parameters as described above.

Only Part 2 will be summarized.

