### 10.3. Scar Assessment

A summary of the Scar Assessment will be provided using the full analysis population. The number and percentage of subjects falling into each response category for the following items will be provided in the summary:

- Subject Asked if Any Scars are Related to Study Treatment (Yes, No)
- Subject Response to Scars Inquiry (Yes, I have scar(s), No, I don't have any scar(s));

And for each scared lesion (TL1, TL2, NTL1, NTL2, NTL3):

Verrica Pharmaceuticals Inc.  
Protocol: VP-315-201

Statistical Analysis Plan  
6-Sep-2024

- Severity of Lesion Scar (Mild, Moderate, Severe)
- Lesion is Most Bothersome to Subject (Yes, No)

The summary will present the above listed parameters within scheduled visit (W1 Safety Assessment, W2 Safety Assessment, EOT).

A separate listing will be provided for the Scar Assessment using the full analysis population, and this listing will include Visit, Date of Visit, and the parameters as described above.

Only Part 2 will be summarized.

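### SCAR-Q, FACE-Q and Scar Assessment answers from treated subjects outside the FA population appear in no planned table or listing, an undeclared departure from the protocol

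*SAP*

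**What the plan says.** SAP Section 10 names one population throughout.

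- **SCAR-Q (10.1):** for the table, "Appearance will be provided using the full analysis population"; for the listing, "Appearance using the full analysis population, and this listing will include Visit, Date of Visit".
- **FACE-Q (10.2):** for the table, "Psychological Function will be provided using the full analysis population"; for the listing, "Psychological Function using the full analysis population, and this listing will include Visit".
- **Scar Assessment (10.3):** "A summary of the Scar Assessment will be provided using the full analysis population". The listing uses the same population.
- **SCAR Scale (10.4):** table and listing are again FA only.

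The first three are presented at the W1 and W2 Safety Assessments and at EOT. The SCAR Scale is presented at EOT only, before excision.

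SAP 6 admits a subject to the FA population only if the subject received one full dose and is among those who "have at least one non-missing post-baseline efficacy observation for histologic clearance of lesions at excision". In Part 1 and in Part 2 Cohorts 4 and 5, a full dose means both injections of the split dose.

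Protocol 11.1 promises: "By-subject listings for all subjects will be provided for data collected". It adds that the SAP will identify where its methods differ from the protocol's. Protocol 9.1 says that data collected before consent is withdrawn are to be included in the analysis. SAP 14, which lists departures from the protocol, does not mention the Section 10 listings. SAP 13 gives the SAP precedence where the two differ.

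**The concern.** These instruments serve an exploratory objective, satisfaction with the treatment. Histology is not needed to score any of them. Yet an answer given a few days after injection is reported only if the subject later supplies an excision specimen with a result and also had a full dose. The Week 1 and Week 2 columns therefore describe satisfaction among subjects who went on to excision, not among those treated and asked.

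The listing matters more than the table. A table restricted to one population is normal when a listing shows everyone. Here the listing has the same filter, so the individual answers of subjects outside the FA population reach no planned output, although the protocol says they will be listed.

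**Working it through.** The SAP gives no figure to reproduce. The check traces who is displayed where.

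**Timing.** Protocol Table 7-1 puts the safety visits at W1D3 and W2D3 in Cohort 4 (Days 3 and 10) and at W1D4 and W2D4 in Cohort 5 (Days 4 and 11, taking W2D4 as 7 + 4). Protocol Table 8-1 puts EOT at Days 84 to 98.

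- Shortest gap from an early answer to excision: 84 − 11 = 73 days, and 73 / 7 = 10.4 weeks.
- Longest gap: 98 − 3 = 95 days, and 95 / 7 = 13.6 weeks.

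So FA status is settled roughly 10 to 14 weeks after these answers are given.

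**Who drops out of the displays.** Applying the SAP 6 definition to each type of treated Part 2 subject:

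- Full dose, excised, histology available: in the FA population; everything is shown.
- Full dose at least once, a later dose partial, excised with histology: still in the FA population; everything is shown.
- Full dose, answered at W1 or W2, withdrew before excision: outside the FA population. The early SCAR-Q, FACE-Q and Scar Assessment answers are shown nowhere. There is no SCAR Scale result to lose.
- Never a full dose (for example, only the first of the two split injections), but returned for excision: outside the FA population. Early and EOT answers, including the SCAR Scale, are shown nowhere.
- Full dose, attended EOT, no histology result: outside the FA population, with the same loss.

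**Does another output restore them?** SAP 5.2 says in general terms that data from the EDC system will be listed. Section 10 then names the FA population for each listing, and the specific statement governs. No other SAP section displays these scales.

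**Comparison with the SAP's other listings.** The excision and PGA listings (8.1, 8.2) use enrolled subjects although their tables use FA. Concomitant medications are tabulated in FA but listed in the Safety Population (7.4). Exposure (7.6), adverse events (9.1) and cutaneous reactions (9.5) are listed in the Safety Population. Only the Section 10 listings apply the histology condition to subject-level data, and no reason is given.

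**Number affected.** This is the number of treated Part 2 subjects outside the FA population with at least one response. The documents do not give it. As an assumption only, if 5% to 20% of the 82 Part 2 subjects fell outside the FA population, that would be 0.05 × 82 = 4.1 to 0.20 × 82 = 16.4, or about 4 to 16 subjects. For any assumed share this is a ceiling. Table 8-1 footnote q has SCAR-Q and FACE-Q completed only by subjects who feel they have treatment-related scars, and protocol 8.5.3 limits FACE-Q to subjects with facial lesions.

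**The case against.** The best defence is that the tables follow the protocol. Protocol 11.4.2 lists SCAR-Q and FACE-Q among the efficacy endpoints, and 11.3 makes the FAS, which already requires a full dose and a histology assessment, primary for efficacy-related data. That stands for those two tables, and it is why they should be kept. It does not extend to the listings. Nor does 11.4.2 name the Scar Assessment or the SCAR Scale.

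A reader might infer several stronger points that the documents do not support:

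- *That satisfaction will be overstated.* No drop-out rate and no score difference is given, and the relevant share is of responders, not of everyone in a cohort. Direction is open too: a subject whose lesion has visibly cleared could decline surgery.
- *That anyone who stops treatment for intolerance is removed.* Protocol 8.3 requires subjects who stop study drug early to return for excision, and 7.4.3 says that Part 2 subjects stopped for a TRAE SI should return for follow-up. Loss needs withdrawal from the study before excision, no full dose at any time, or no histology result.
- *That the SCAR Scale loses Week 1 answers.* It has none; it is an EOT assessment.
- *That the exclusions are invisible.* SAP 7.1.1 tabulates the number in each population with reasons for exclusion and lists each subject's population membership. What is missing is the answers themselves.

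It is also fair that the local tolerability of subjects who leave is still reported in the Safety Population through adverse events and cutaneous reactions, and that the questionnaire data remain in the database.

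**Conclusion.** The point holds as a reporting gap. For SCAR-Q, FACE-Q and the Scar Assessment, a treated subject who answered early and then withdrew before excision, or who never had a full dose, appears in no planned table or listing. For the SCAR Scale the gap is confined to subjects who attend EOT but never had a full dose or have no histology result. The FA-only listings contradict protocol 11.1 and, for subjects who withdraw consent, 9.1. The departure is undeclared, and SAP 13 would let it stand.

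The FA tables for SCAR-Q and FACE-Q are not an error against the protocol. Their limitation is that the Week 1 and Week 2 summaries depend on a later event that the scales do not need.

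The impact is minor: the endpoints are exploratory, the analyses are descriptive, and no test is affected. This verdict rests on reading the population named in each Section 10 listing as overriding the general statement in SAP 5.2.

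**What to change.** - In SAP 10.1 to 10.4, change the listing population to the Safety Population. Every one of these assessments follows the first injection, so this captures every subject who could have an answer.
- In SAP 10.1 to 10.3, keep the FA tables and add summaries at W1, W2 and EOT of all treated subjects with a response at that visit, with the number responding shown. For 10.4 the listing change is enough.
- In SAP 14, record the added summaries. If the FA-only listings are kept instead, declare them there with a reason.

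The cost is SAP wording and a population flag; no new data are needed. The downside is that a few subjects with only early-visit data enter the added summaries, so the responders differ between visits and the visit means should not be read as within-subject change. If the database is already locked, SAP 5.2 requires added analyses to be labelled post hoc.

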## 10.2. FACE-Q – Psychological Function

A summary of FACE-Q – Psychological Function will be provided using the full analysis population. Descriptive statistics will be provided for Raw Sum (10 = Worst to 40 = Best) and Score (0 = Worst to 100 = Best). The number and percentage of subjects falling into each scale level (1 = Definitely disagree, 2 = Somewhat disagree, 3 = Somewhat agree, 4 = Definitely agree) for responses to the following ten assessment statements will be provided in the summary:

- a. I like myself
- b. I feel positive about myself
- c. I feel okay about myself
- d. I feel happy
- e. I am comfortable with myself
- f. I am accepting of myself

Verrica Pharmaceuticals Inc.  
Protocol: VP-315-201

Statistical Analysis Plan  
6-Sep-2024

- g. I feel good about myself
- h. I feel confident
- i. I feel attractive
- j. I feel great about myself

Raw Sum is calculated as follows:

- If the number of missing responses is 0, then Raw Sum is the total of the numeric response values.
- If the number of missing responses is  $>0$  and  $<5$ , then Raw Sum is  $[(\text{number of missing responses} \cdot \text{mean of non-missing response}) + \text{total of non-missing numeric response values}]$ .
- If the number of missing responses is  $\geq 5$ , then Raw Sum is missing.

Score is calculated as follows:

- If Raw Sum is missing, then Score is missing.
- Otherwise, Score is provided by the FACE-Q Conversion Table.

The summary will present Raw Sum, Score, and the above listed statements within scheduled visit (W1 Safety Assessment, W2 Safety Assessment, EOT).

A separate listing will be provided for FACE-Q – Psychological Function using the full analysis population, and this listing will include Visit, Date of Visit, and the parameters as described above.

Only Part 2 will be summarized.

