# 3. OBJECTIVES

In this 2-part study, the following objectives and endpoints will be evaluated when administered intratumorally to adult subjects  $\geq 18$  years of age with biopsy-proven BCC:

Part 1		
Primary Objectives	Endpoints	
To assess the safety, tolerability, and MTD of ascending dose strengths of VP-315	
 
Discontinuations due to AEs; occurrence of DLTs
 
CRA
 
	
Exploratory Objectives	Endpoints	
To evaluate the objective antitumor efficacy of VP-315	
 
Histological clearance of treated lesion(s) at excision
 
Clinical clearance of treated lesion(s) at excision as determined by visual assessment (no tumor seen upon visible inspection)
 
Estimate of remaining tumor volume (necrotic cells:tumor cells) at excision
 
Abscopal effect as determined by clinical and histological clearance of nontreated lesions at excision
 
PGA
 
	
Part 2 (Coh	orts 1 and 2)	
Primary Objectives	Endpoints	
To determine the optimal regimen for dosing 8 mg of VP-315 based on safety and tolerability	
 
Treatment-related AEs; treatment-related serious adverse events (SAEs); discontinuations due to AEs; occurrence of TRAEs of special interest
 
CRA
 
	
Secondary Objectives	Endpoints	
To evaluate the antitumor efficacy of VP-315	
 
Clinical clearance of treated lesion at excision as determined by visual assessment (no residual tumor seen on visual inspection)
 
Histological clearance of target lesion(s) at excision
 
Abscopal effect as determined by clinical and histological clearance of non-target lesions at excision
 
Estimate of remaining tumor volume (necrotic cells:tumor cells) at excision
 
PGA
 
	

Exploratory Objectives	Endpoints	
To assess the immune response to VP-315 treatment in a subset of subjects by assessing the immune repertoire in blood and in tissue	
 
Multiplex immunohistochemical staining for T-cell subsets and immune activation markers in tumor tissue sample
 
Analysis of T-cell clonality in blood and tumor tissue samples
 
	
To assess subject satisfaction with the treatment	• SCAR-Q, FACE-Q	
Part 2 (Cohorts 4 and 5)		
Primary Objectives	Endpoints	

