To gain additional information on the safety, tolerability and dosing regimen of VP-315 to support a pivotal study protocol design	
 
Treatment-related AEs; treatment-related serious adverse events (SAEs); discontinuations due to AEs; occurrence of TRAEs of special interest
 
CRA
 
	
Secondary Objectives	Endpoints	
To confirm the antitumor efficacy of VP- 315 using the optimal dosing regimen determined in Part 2	
 
Clinical clearance of treated lesion at excision as determined by visual assessment (no residual tumor seen on visual inspection)
 
Histological clearance of treated lesion(s) at excision
 
	
	Abscopal effect as determined by clinical and histological clearance of nontreated lesions at excision	
	
 
Estimate of remaining tumor volume (necrotic cells:tumor cells)
 
PGA
 
	
To characterize the pharmacokinetics (PK) of an 8 mg dose of VP-315 administered with the optimal dosing regimen	Plasma VP-315 concentrations	

Exploratory Objectives	Endpoints				
To assess subject and physician satisfaction with the treatment	
 
SCAR-Q, FACE-Q
 
Scar Cosmesis Assessment and Rating (SCAR) Scale
 
				
To assess the immune response to VP-315 treatment in a subset of subjects by assessing the immune repertoire in blood and in tissue	
 
Multiplex immunohistochemical staining for T-cell subsets and immune activation markers in tumor tissue samples
 
Analysis of T-cell clonality in blood and tumor tissue samples
 
				

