- o. Blood samples for PK assessments will be collected on the first day of full target dose administration immediately prior to the VP-315 dose and at 2- and 5-minutes post first injection and 2-, 5-, 10-, 20-, 30-, 60-, and 120-minutes post last injection; samples will also be collected on the following day 24 hours (±1 hour) post prior injection of VP-315. Blood samples for PK assessments will only be collected for subjects in Part 2 (Cohorts 4 and 5 expansion groups).
- p. Photography of BCC lesion taken by a study team member prior to each treatment through EOS. Evaluation of lesion necrosis by the SRC (Part 1) or Medical Monitor (Part 2) is required for continued treatment.
- q. Subjects in Part 2, will complete SCAR-Q and FACE-Q if they feel they have scars related to study treatment (relevant subscales only) at Safety Assessment Visits, and EOT.
- r. Subjects will return approximately 7- or 14-days after excision (EOS) for a postsurgical assessment (7 days on the face and 14 days on the body). Subjects with excised lesions on both the face and the body will be required to complete 2 EOS visits accordingly.
- s. Subjects with AE(s) at the EOS visit will be contacted by phone at least 30 days after the EOS visit to confirm the status of any ongoing AE(s).
- t. Limited Safety Assessment Visit conducted only in Part 2
  - a. Cohorts 1-2: If the treated lesion is not fully necrosed at the W2D4 Safety Assessment Visit, a Limited Safety Assessment Visit should occur on W3D1 for further evaluation of the lesion for necrosis. No additional treatment will be adminstered.
  - b. Cohorts 4-5 (including expansion groups): If only 1 target lesion is treated and complete necrosis is not achieved at the W1 Safety Assessment Visit, subjects should return on W2D1 for further evaluation of the lesion for necrosis. No additional treatment will be administered. If a second target lesion was treated and complete necrosis is not achieved at the W2 Safety Assessment Visit, subjects should return on W3D1 for further evaluation of the lesion for necrosis. No additional treatment will be administered.
- u. Scar Cosmesis Assessment and Rating (SCAR) Scale will be completed by the site investigator prior to excision at the EOS Visit.

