## 8.5.3 Subject-reported Outcomes

In Part 2 of the study, subject-reported outcomes will be collected with the SCAR-Q (Scar appearance, Scar symptoms, and Psychosocial impact scales) (Appendix 3) and relevant subscales of the FACE-Q (Appendix 4) (Satisfaction with outcome) completed at each Safety Assessment Visit, and EOT visit.

The FACE-Q will only be completed by subjects who have target or nontarget lesions on the face.

Brief instructions are provided at the start of each scale, and questionnaires will be administered via electronic Patient Reported Outcomes tablets during the subject visit in accordance with Table 8-1.

Each SCAR-Q and FACE-Q scale provides 4 response options that measure frequency. All scales use a 4-point scale. There is no overall or total score, only scores for each independent scale. Each scale is transformed into scores that range from 0 to 100. The scores are computed from the responses to the items by adding them together and converting the raw score to a scale from 0 to 100. Higher scores reflect a better outcome.

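### SAP Section 10 replaces the protocol's FACE-Q satisfaction scale with Psychological Function and omits two of three SCAR-Q scales, undeclared, so no analysed scale directly measures subject satisfaction with outcome

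*SAP*

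**What the plan says.** The objective is exploratory. For Part 2 Cohorts 1 and 2, Protocol Section 3 words it as "To assess subject satisfaction with the treatment", with SCAR-Q and FACE-Q as endpoints. For Cohorts 4 and 5 it is "To assess subject and physician satisfaction with the treatment", and the clinician-completed SCAR Scale is added as an endpoint. These tables name instruments, not scales.

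The scales are named in the procedures. Protocol 8.5.3 specifies "SCAR-Q (Scar appearance, Scar symptoms, and Psychosocial impact scales) (Appendix 3) and relevant", continuing directly with "subscales of the FACE-Q (Appendix 4) (Satisfaction with outcome) completed at each Safety Assessment Visit, and EOT visit". Protocol 8.2 names the same four scales.

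Two conditions govern who answers. Table 8-1 footnote q says Part 2 subjects "will complete SCAR-Q and FACE-Q if they feel they have scars related to study treatment". Protocol 8.5.3 separately limits FACE-Q to subjects with a target or nontarget lesion on the face.

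SAP Section 10, headed as the treatment satisfaction analysis, contains four summaries:
- 10.1: SCAR-Q, Appearance scale only.
- 10.2: "A summary of FACE-Q – Psychological Function will be provided using the full analysis population".
- 10.3: a Scar Assessment, including whether the subject reports having scars.
- 10.4: the SCAR Scale, for Cohorts 4 and 5 and their expansions.

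Protocol 11.1 undertakes that the SAP will identify where its methods depart from the protocol. SAP 14 is that list, and SAP 13 gives the SAP precedence.

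**The concern.** The one protocol scale with satisfaction in its name is absent from the SAP, and a scale about how subjects feel about themselves stands in its place under the satisfaction heading. Because the SAP prevails and does not declare the change, a reader of the study report could take a Psychological Function score as the answer on treatment satisfaction. Two SCAR-Q scales, symptoms and psychosocial impact, also drop out without comment.

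A second, smaller matter concerns who the means describe. SAP 10.1 and 10.2 name the full analysis population and mention neither the scar condition nor the facial-lesion condition. SAP 5.6 provides for no imputation beyond what individual sections specify, and the rules in 10.1 and 10.2 only fill in missing items within a mostly completed questionnaire. Subjects who did not complete a questionnaire therefore contribute nothing to its mean, and the tables as specified would not say so.

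At stake is what this exploratory objective can conclude and how the tables are labelled.

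**Working it through.** No sample size, power or error rate is involved, since SAP 5.2 plans no formal inference. The check is a comparison of scales, after confirming that the SAP's scoring ranges fit the items it lists.

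**Scoring ranges (number of items × lowest and highest response code)**
- FACE-Q Psychological Function: 10 × 1 = 10 to 10 × 4 = 40. SAP 10.2 gives 10 to 40.
- SCAR-Q Appearance: 12 × 1 = 12 to 12 × 4 = 48. SAP 10.1 gives 12 to 48.
- SCAR Scale: clinical items 4 + 3 + 1 + 1 + 3 + 1 = 13; with two patient items, 13 + 2 = 15. SAP 10.4 gives 13 and 15.

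All three agree, so the SAP describes complete scales, and Psychological Function is the scale actually specified in 10.2.

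**Scales side by side**

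| Scale | Protocol 8.2 and 8.5.3 | SAP Section 10 |
|---|---|---|
| SCAR-Q Appearance | named | summarised (10.1) |
| SCAR-Q Symptoms | named | absent |
| SCAR-Q Psychosocial impact | named | absent |
| FACE-Q Satisfaction with outcome | named | absent |
| FACE-Q Psychological Function | not named | summarised (10.2) |

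Of 3 + 1 = 4 named scales, 1 is summarised and 3 are omitted; 1 unnamed scale is added.

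**Item content of SAP 10.2.** The ten statements cover self-liking, self-acceptance, happiness, confidence and attractiveness. Items about the treatment or its outcome: 0 of 10.

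**Declaration.** SAP 14 has six entries: reduction in tumor volume, the definition of enrolled subjects, the form of the remaining-volume estimate, the DLT and TRAE SI observation periods, laboratory shift categories, and PK metabolites. None concerns Section 10.

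**What subject-reported content remains**
- All Part 2 cohorts: SCAR-Q Appearance (how much the subject is bothered by features of the scar) and the Scar Assessment in 10.3.
- Cohorts 4 and 5 only: two yes/no patient items in the SCAR Scale, on itch and pain. By the SAP's counts these cohorts hold 36 + 37 = 73 of 82 Part 2 subjects (89%).
- Cohorts 1 and 2: 6 + 3 = 9 subjects, without the SCAR Scale.

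All of this is about scars. None of it asks whether the subject is satisfied with the treatment outcome.

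**Who answers.** Footnote q restricts both questionnaires to subjects who feel they have treatment-related scars; 8.5.3 adds the facial-lesion limit for FACE-Q. SAP 10.3 already counts subjects who say they have no scars, in the same population, at the same three visits (Week 1 and Week 2 Safety Assessments and EOT) and for Part 2. The count is therefore planned, but 10.1 and 10.2 do not refer to it.

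**The case against.** The strongest reply is that the objective is still served. The objectives tables name only the instruments, and a scale from each instrument is reported. SCAR-Q Appearance, a protocol-named scale, is kept. SAP 10.3 adds subject-reported scar information. SAP 10.4 analyses the SCAR Scale, a named endpoint for Cohorts 4 and 5, where the objective includes physician satisfaction and where the itch and pain items touch on symptoms.

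This stands against a reading that a reader might be tempted to make, namely that the satisfaction objective goes unanswered. The documents do not support that: the physician part is covered in Cohorts 4 and 5, and the subject part is addressed indirectly through scars. It does not meet the narrower point. Protocol 8.2 and 8.5.3 agree on the scales, and neither the scar items nor Psychological Function asks about satisfaction with outcome. The protocol's reference to relevant FACE-Q subscales might seem to leave room for others, but the only one it names is the one omitted.

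A reader might also infer that the best outcomes are missing from the means because subjects without scars do not answer. The documents do not show this. Having no scar is not the same as being satisfied, Protocol Appendix 3 presents SCAR-Q as an instrument for people with scars, and 8.2 and 8.5.3 state no scar condition. What stands is that the tables should say whom they describe.

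Finally, the omitted scales may never have been collected. SAP 5.2 promises listings of collected data, and Section 10 lists none of these scales. That is suggestive but not conclusive, and it bears on which remedy applies rather than on whether one is needed.

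**Conclusion.** The concern holds in this form. The SAP substitutes one patient-reported scale and omits two others that the protocol names, without declaring it where the protocol says differences will be identified. As written, no scale in the SAP directly measures subject satisfaction with the treatment outcome, and the subject-reported part of the objective rests on scar items alone.

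The consequence is limited. The objective is exploratory and the analysis descriptive, so primary safety and secondary efficacy conclusions do not change. What changes is what may be said about satisfaction: the 10.2 table can support a statement about psychological function among those who completed it, and no more.

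This rests on reading the protocol's procedures sections as the specification of the scales, and on the documents being silent about which scales were administered.

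**What to change.** 1. If FACE-Q Satisfaction with outcome and SCAR-Q Symptoms and Psychosocial impact were collected, add their summaries to SAP Section 10, at the visits and in the population already used there.
2. If they were not collected, list the FACE-Q substitution and the two SCAR-Q omissions in SAP 14. Do not report Psychological Function as treatment satisfaction, and state that subject satisfaction with outcome was not directly assessed.
3. In the SCAR-Q and FACE-Q tables, state that the means apply to subjects who completed the questionnaire: those reporting treatment-related scars (Table 8-1 footnote q) and, for FACE-Q, those with facial lesions (Protocol 8.5.3). Refer to the no-scar count already tabulated in SAP 10.3; no new count is needed.

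The cost is a few extra descriptive tables if the data exist, or a short SAP 14 entry and relabelling if they do not, plus table footnotes in either case. No new data collection is needed.
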